9.2 Schedule

Protocol: ARO-005

Patients will be treated according to the following schedule:

- The starting dose will be 100 mg TID. Dose reductions for adverse events are listed in table 10.2.
- Dose reduction guidelines for adverse events are listed in table 10.2 and 10.3 in Section 10.2. Dose reductions beyond those mentioned in these tables or different than those specified, should be discussed with the sponsor and documentation of the justification recorded.
- One cycle of therapy is defined as 28 consecutive days regardless of whether study drug is taken or not.
- Subsequent cycles may be delayed for recovery of toxicity. Delays in start of subsequent cycles greater than 8 weeks will be acceptable only for patients who are deriving clinical benefit and after determination of the principal investigator of potential risk/benefit ratio.
- If prolonged (more than 60 days) grade 4 neutropenia or thrombocytopenia with evidence of a hypocellular marrow (marrow cellularity less than 5% without evidence of leukemia) is observed, protocol treatment may be interrupted until recovery to ANC $> 0.5 \times 10^9$ /L and platelets $> 25 \times 10^9$ /L . If the peripheral counts do not recover ANC $< 0.5 \times 10^9$ /L and/or platelets $< 25 \times 10^9$ /L but there is evidence of residual leukemia in the bone marrow, subsequent cycles can be administered at the discretion of the investigator.
- For patients who discontinue therapy, the reason for treatment discontinuation will be captured.

9.3 Crenolanib Administration

- Prophylactic antiemetic therapy is recommended to be used as needed for nausea and/or vomiting.
- If a dose is missed or vomited, it should not be taken again. The next dose should not be increased to account for missing a dose. The patient should take the next regular dose at the regularly scheduled time.

9.4 **Duration of Therapy**

Treatment may continue until one of the following criteria applies:

- 1. Clinically significant progressive disease, or
- 2. Intercurrent illness that in the opinion of the investigator prevents further administration of treatment, or
- 3. Patient request, or
- 4. General or specific changes in the patient's condition render the patient unacceptable for further treatment in the judgment of the investigator, or
- 5. Unacceptable toxicity that in the opinion of the investigator makes it unsafe to continue therapy, or
- 6. Treatment interruption due to toxicity that has not recovered to at least grade 1 within 8 weeks

It is planned that up to a total of 12 cycles of therapy will be administered for patients deriving benefit from this regimen. Continuation of therapy for patients completing 12 cycles of therapy may be considered on a case by case basis after discussion with the sponsor's medical monitor.

A minimum of 1 full course (defined as the administration of crenolanib for 28 days) will be required for a patient to be considered as having received an adequate trial to evaluate efficacy. Patients who do not complete one cycle of crenolanib therapy will be replaced. All patients receiving at least one dose of study drug will be considered evaluable for toxicity.

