7. STUDY DESIGN

This is a Phase II open label study of crenolanib besylate given at 100 mg TID (preferably every eight hours) continuously until one of the criteria for study discontinuation is fulfilled. Study drug should be taken at least 30 minutes prior to or following a meal. Patients will complete a daily diary to record the date, time, and amount (number of tablets) of crenolanib taken and relation to eating schedule (Appendix IV).

The study will enroll 2 different cohorts of patients in parallel.

Cohort A: Will enroll AML patients with FLT3 activating mutations who have progressed on one or more prior chemotherapy regimen who have not received previously a FLT3 TKI

Cohort B: Will enroll AML patients with FLT3 activating mutations whose leukemia has progressed and have received prior therapy with one or more FLT3 TKIs.

Cycles will be repeated approximately every 28 days, and therapy will be continued until clinically significant disease progression or documentation of unacceptable toxicity as determined by the investigator. If the drug is discontinued for toxicity, patient should be reassessed until toxicity has resolved.

In the setting where hematopoietic stem cell transplant is anticipated study drug will be discontinued at least 72 hours prior to start of conditioning.

Counting Cycle Days: If drug is held or a dose missed, the missed/held dose should not be made up. Dosing will resume with the next scheduled dose. The patient should enter in the diary the doses missed. If drug is held for a day or more, the counting of cycle days should continue as if uninterrupted. The start of cycle 1 is denoted by the ingestion of study drug. The scheduled procedures/visits should comply with the study calendar regardless of amount of study drug administered in a 28 day cycle.

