9. TREATMENT PLAN

9.1 General

The study will enroll patients with primary AML relapsed/ refractory after prior therapy, secondary AML (due to prior chemo- or radiation therapy) or prior transformed MDS/MPN with FLT3 activating mutations. Patients will be treated with crenolanib three times daily, preferably every eight hours, continuously until they fulfill one of the criteria for study discontinuation. The objective will be to administer crenolanib at full dose starting at 100 mg TID. Other dose levels will be used for dose adjustments for toxicity (refer to section 10) during therapy. The only exception to this will occur on course 1 day 1, when doses 2 and 3 will be held in order to analyze the pharmacokinetics of the first dose administered out to 24 hours.

Patients currently enrolled at 100mg TID (protocol v1.1) may be dose escalated based on BSA, see table 10.2.

Up to 70 evaluable patients will be enrolled on this study: 30 patients in Cohort A and 40 patients in Cohort B. Patients receiving less than 28 days of study dug will be replaced for efficacy evaluation. All patients will be assessed for toxicity.

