10.2 Dose Reductions for Non-Hematologic Toxicities

Dose reductions for non-hematologic toxicities due to crenolanib, will be done according to the schema outlined in Table 10.1.

• Reductions below 60mg TID are not planned; dose reductions beyond those mentioned in this table or different than those specified, should be discussed with the sponsor and documentation justifying the specified dose recorded. If an appropriate dose is not determined, then it will lead to patients' withdrawal from the study drug, in which the patient will stop taking crenolanib, but will still be followed for outcomes.

Dose level	Crenolanib dosing
0	100 mg TID
-1	80 mg TID
-2	60 mg TID

Table 10.2. Crenolanib dose reduction guidelines

Toxicity	Dose Modification
(NCI Criteria)	
Grade 1 or 2	No dose modification
Clinically significant	Hold drug until toxicity resolves to grade 1 or less. Restart drug
persistent grade 2	at same dose level (Table 10.2).
despite optimal therapy	

Hold drug until toxicity resolves to grade 1 or less. Restart drug
at next lower dose level (Table 10.2).

Table 10.3. Crenolanib dose reduction guidelines for All Toxicities (except GI (nausea, vomiting and diarrhea)) related to study drug.

Starting dose (dose level 0) for all patients will be 100 mg TID. A maximum of two (2) dose reductions are allowed in a single patient for toxicity management.

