The number of tablets taken will be determined by counting the number of tablets returned at each visit and subtracting that number from the number of tablets dispensed. The number of tablets expected to be taken will be determined by the assigned dose and taking into account any prescribed dose reductions and omissions.

No minimal level of compliance will be defined for patient inclusion in efficacy analyses. An exploratory analysis of compliance may be performed by regressing percent compliance on selected efficacy endpoints. If significant results are indicated, analysis may be performed to determine the level of compliance that best delineates each endpoint.

Criteria for End of Study

Protocol: ARO-005

This study will be considered complete following the data cut-off date for the final analysis. Documentation of the data cut-off will be included in the master study file.

After the final analysis, if patients are continuing to benefit from study treatment, they will be allowed to continue receiving study treatment. If patients continue on crenolanib beyond study closure, safety data must be collected. If further data are collected that are not included as part of the final locked database, the post hoc data will eventually be combined with the locked database and stored in a data library separate from the locked database.

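### Sections 9.1 and 9.4 define efficacy evaluability both by 28 days of drug received and by 28 calendar days, so patients with held or missed days who are assessed after cycle 1 and then stop can be either replaced or counted

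*Combined protocol and SAP*

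**What the plan says.** Two passages count drug received:

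- Section 9.1: "Patients receiving less than 28 days of study dug will be replaced for efficacy evaluation".
- Section 9.4, first sentence of the closing paragraph: "A minimum of 1 full course (defined as the administration of crenolanib for 28 days) will be required for a patient to be considered" to have had an adequate trial for efficacy.

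Three passages, read together, count calendar time:

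- Section 9.4, the very next sentence: "Patients who do not complete one cycle of crenolanib therapy will be replaced".
- Section 9.2: "One cycle of therapy is defined as 28 consecutive days regardless of whether study drug is taken or not".
- Section 7: "If drug is held for a day or more, the counting of cycle days should continue as if uninterrupted". The same paragraph says held or missed doses are not made up.

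Section 16.4, under Treatment Compliance, adds: "No minimal level of compliance will be defined for patient inclusion in efficacy analyses".

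Holds are foreseen. For qualifying toxicities Table 10.3 says: "Hold drug until toxicity resolves to grade 1 or less". The planned numbers are evaluable patients: "Up to 70 evaluable patients will be enrolled on this study: 30 patients in Cohort A and 40 patients in Cohort B". Sections 16.1 and 16.3 give the decision rules and the confidence interval but do not say which patients form the denominator.

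**The concern.** The primary endpoint is a response rate judged against small pass marks: 5 of 40 in Cohort B and 4 of 30 in Cohort A, with stage 1 continuing on 2 responders. Who occupies those 40 and 30 places therefore matters.

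Two adjacent sentences of 9.4 give different answers for the same patient. The group affected is unlikely to be a random sample. Non-responders tend to be taken off after the first marrow, and some responders may leave for transplant, for which Section 7 requires drug to stop before conditioning. Replacing the former raises the apparent response rate; replacing the latter lowers it. The trial is open label and the protocol does not choose between the readings, so the choice could be made after responses are known.

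**Working it through.** **1. The passages applied to one patient.** Count any day with at least one dose as a drug day. A patient has five days held in cycle 1, so at day 28 there are 28 - 5 = 23 drug days.

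- *Stops at cycle 2 day 1 after the marrow.* Under 9.1 and the first sentence of 9.4, 23 is below 28 and the patient is replaced. Under the second sentence of 9.4 with 9.2 and Section 7, one cycle is complete and the patient is counted. The rules conflict.
- *Continues into cycle 2 without a further hold.* The 28th drug day falls on day 28 + 5 = 33. Neither drug-received passage requires the 28 days to lie inside the first cycle, so this patient is evaluable under both rules.

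The conflict is therefore limited to patients with held or missed days who reach day 28, are assessed, and stop before 28 drug days.

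**2. The plan's own figures.** Inputs are from Section 16.1.

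- Early termination at 5%, formula 0.95^n1 + n1 × 0.05 × 0.95^(n1-1). Cohort B (n1 = 28): 0.238 + 0.350 = 0.588, stated 59%. Cohort A (n1 = 24): 0.292 + 0.369 = 0.661, stated 66%.
- P(declared active) = sum over x ≥ 2 of P(X1 = x) × P(X2 ≥ r - x), where X1 is binomial on n1, X2 is binomial on n - n1, and r is the pass mark.
- Cohort B (28/40, r = 5): type I error 0.047, power 0.921 at 20%. Cohort A (24/30, r = 4): type I error 0.060, power 0.990 at 30%.

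Both designs reproduce. They presuppose a settled denominator.

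**3. Effect of replacing the group in step 1.** Let hN and hR be the shares of non-responders and responders replaced. A true rate p appears among evaluable patients as

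q = p(1 - hR) / [p(1 - hR) + (1 - p)(1 - hN)].

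The documents give neither share, so the values below are assumptions.

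| hN | hR | q when p = 0.05 | Type I error, B | Type I error, A |
|---|---|---|---|---|
| 0 | 0 | 0.0500 | 0.047 | 0.060 |
| 0.05 | 0 | 0.05/0.9525 = 0.0525 | 0.056 | 0.069 |
| 0.10 | 0 | 0.05/0.905 = 0.0552 | 0.067 | 0.080 |
| equal | equal | 0.0500 | 0.047 | 0.060 |

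The opposite direction, with responders lost and no non-responders, lowers power. In Cohort B with hR = 0.05, q = 0.19/0.99 = 0.192 and power is 0.902. With hR = 0.10, q = 0.18/0.98 = 0.184 and power is 0.878. The starting value is 0.921.

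**The case against.** The strongest reply is that 28 days is shorthand for completing cycle 1, as the adjacent sentence of 9.4 suggests, and that 9.2 defines a cycle rather than an analysis population. That may well be the intent. However, 9.1 speaks of drug received, 9.4 of drug administered, and 9.2 expressly separates the cycle from drug taken. The text does not settle the matter, and writing the intent down is all that is asked.

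Several stronger readings are tempting but unsupported:

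- **A reader might infer that anyone with a held day in cycle 1 is replaced, even in remission.** Step 1 shows otherwise: a patient who stays on treatment normally reaches 28 drug days in cycle 2.
- **A reader might take 16.4 as a third definition that collides with toxicity holds.** Its expected tablet count already allows for prescribed reductions and omissions, so a prescribed hold does not lower compliance. It conflicts with 9.1 only for doses missed without being prescribed. It could also be read as applying only within patients already evaluable, though it does not say so.
- **A reader might infer from Section 6 that no patient received the full planned amount**, because the highest delivered dose at 100 mg TID was 298 of 300 mg/day. Section 9.1 withholds two doses on day 1. If these count as undelivered, a fully adherent patient averages (27 × 300 + 100)/28 = 292.9 mg/day over 28 days and (99 × 300 + 100)/100 = 298 over 100 days. The maximum is compatible with no toxicity hold. Section 6 also pools two studies, mixes reductions with delays, and is not stated to be cycle 1 data.
- **A reader might assume that 15-30% of patients are affected.** No figure in the documents supports this. Section 10.3 plans no cycle 1 interruptions for myelosuppression, and Table 10.3 excludes nausea, vomiting and diarrhea, the most frequent non-hematological grade 1/2 toxicities reported in Section 5. Both suggest fewer holds.

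**Conclusion.** The inconsistency is real but narrow. It affects patients with held or missed days who have the end-of-cycle-1 assessment and stop short of 28 drug days. It bears on the primary endpoint because Section 16 names no efficacy set. The sizes in step 3 illustrate sensitivity to assumed shares and directions and do not estimate what will happen in this trial: the inflation of roughly 0.01 to 0.02 in type I error requires that only non-responders are replaced. The case for acting rests on the contradiction and on how little it costs to remove, more than on the size.

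**What to change.** Reword 9.1 and the first sentence of the 9.4 paragraph to use the 9.2 cycle. A patient who has not discontinued by day 28 of cycle 1, or who has an end-of-cycle-1 response assessment, is evaluable for efficacy and is not replaced because of held, missed or reduced doses. A cross-reference in 16.3 would then fix the denominator where the analysis is described.

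The cost is two sentences. The downside is that some less-exposed patients stay in the denominator, including the occasional patient held for most of the cycle, and the response rate may move slightly in either direction. No dosing or hold rule changes.

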9.5 Concomitant Medications

Protocol: ARO-005

In general, the use of any concomitant medication/therapies deemed necessary for patient supportive care and safety are permitted. Other anticancer agents including systemic chemotherapy, radiation therapy, or biologic response modifiers are not permitted during the study, with the exception of hydroxyurea which is allowed for 14 days anytime during the first 28 days on study.

Prophylactic intrathecal therapy is allowed to prevent recurrence of CNS disease. Patients with active CNS disease are excluded.

No other investigational drugs are allowed during the study without consent of the medical monitor.

10. DOSING AND DOSE MODIFICATIONS OF CRENOLANIB

Toxicities will be graded using the NCI CTCAE, Version 4.03 (see partial representation in Appendix VII).

The starting dose for all patients will be 100 mg TID.

10.1 Dose Escalation

There will be one level dose escalation allowed for patients who do not experience grade 3 or 4 toxicity and who have no response based on investigator evaluation.

Dose level	Crenolanib dosing
0	100 mg TID
+1	120 mg TID

Table 10.1. Crenolanib dose escalation guidelines

Dose escalation can occur as early as cycle 1 day 15.

10.2 Dose Reductions for Non-Hematologic Toxicities

Dose reductions for non-hematologic toxicities due to crenolanib, will be done according to the schema outlined in Table 10.1.

• Reductions below 60mg TID are not planned; dose reductions beyond those mentioned in this table or different than those specified, should be discussed with the sponsor and documentation justifying the specified dose recorded. If an appropriate dose is not determined, then it will lead to patients' withdrawal from the study drug, in which the patient will stop taking crenolanib, but will still be followed for outcomes.

Dose level	Crenolanib dosing
0	100 mg TID
-1	80 mg TID
-2	60 mg TID

Table 10.2. Crenolanib dose reduction guidelines

Toxicity	Dose Modification
(NCI Criteria)	
Grade 1 or 2	No dose modification
Clinically significant	Hold drug until toxicity resolves to grade 1 or less. Restart drug
persistent grade 2	at same dose level (Table 10.2).
despite optimal therapy	

Hold drug until toxicity resolves to grade 1 or less. Restart drug
at next lower dose level (Table 10.2).

Table 10.3. Crenolanib dose reduction guidelines for All Toxicities (except GI (nausea, vomiting and diarrhea)) related to study drug.

Starting dose (dose level 0) for all patients will be 100 mg TID. A maximum of two (2) dose reductions are allowed in a single patient for toxicity management.

10.3 Dose Reductions of Crenolanib for Hematologic Toxicities

Patients with leukemia usually present with abnormal peripheral blood counts at the time therapy is started and myelosuppression is an expected event during the course of therapy for acute leukemia. Thus, no dose adjustments or treatment interruptions for myelosuppression will be planned for the first cycle of therapy. After this time, treatment interruptions and dose adjustments may be considered according to the following guidelines:

Patients with neutropenia or thrombocytopenia as a consequence of the disease do not require treatment interruptions for myelosuppression. Dose-reductions in these patients should be considered in an individual case and discussed with the medical monitor. The following guidelines can be used for these patients:

- Patients with pre-cycle counts of neutrophils >1x10⁹/L and platelets >100 x10⁹/L and no evidence of residual leukemia who have sustained neutropenia <0.5 x10⁹/L or platelet counts <25 x x10⁹/L for more than 4 consecutive weeks in the current cycle, may receive a subsequent cycle at 1 dose level reduction. A reduction of 2 dose levels may be considered if the myelosuppression was deemed severe and life threatening by the treating physician, and if it is in the patient's best interest.
- If there are persistent peripheral blood blasts, or the bone marrow shows >5% blasts, treatment may continue regardless of neutrophil and platelet count with supportive care as needed.
- Patients with pre-cycle counts of neutrophils $<1x10^9/L$ and platelets $<100 x10^9/L$ and no evidence of residual leukemia, consider holding therapy until recovery of granulocytes to $\ge 1 x10^9/L$ and platelets $\ge 60 x10^9/L$, then resume at same or 1 lower dose level according to guidelines mentioned in Table 10.2.

10.4 Additional Dose Modifications requiring discussion with Sponsors Medical Monitor

Modification of dose schedules for toxicities other than the above will be allowed within the following guidelines:

- Dose reductions beyond dose level (-2) should be discussed with the sponsor and documentation of the justification recorded.
- Dose adjustments by more than 1 dose level at a time can be considered when judged in the best interest of the patient (e.g., neutropenia with sepsis, bleeding requiring platelet transfusions) when toxicity has resolved. The reason for this reduction will be reviewed by the PI and documented in the medical record. Dose re-escalation may be reconsidered.

Protocol: ARO-005

30

10.5 Dose Re-escalation

• A patient who has had a dose reduction for any reason may have their dose re-escalated provided the patient has remained free of toxicity requiring dose adjustments for at least 1 month. Escalation will be made by 1 dose-level increments only, and not more frequent than every cycle. Re-escalation cannot exceed the patient's previous highest dose..

10.6 Cycle Delays

Protocol: ARO-005

- A cycle of therapy may be delayed for a maximum of 8 weeks to allow recovery from toxicities.
- Inability to re-start therapy within 8 weeks after a treatment interruption for toxicity will constitute grounds for removing the patient from protocol.

10.7 Continued Access to Study Drug

At AROG's discretion, patients receiving crenolanib at the time of study closure may continue to receive crenolanib until disease progression or initiation of other therapy. However, if a serious adverse event (SAE) occurs during this time, AROG may request additional information (such as local lab results, concomitant medications, and hospitalizations) in order to evaluate the reported SAE.

11. AGENT FORMULATION AND PROCUREMENT

11.1 Dose preparation and Storage of Crenolanib

Crenolanib is supplied as 100 mg and/or 20 mg tablets for oral dosing, in 42-count bottles or 30-count bottles. Crenolanib tablets should be refrigerated at a temperature between 2°C and 8°C (35.6°F and 46.4°F). Standard household refrigeration is considered adequate for drug storage. Crenolanib should be stored in the vials provided by the pharmacy and kept out of the reach of children.

Used bottles and unused tablets and bottles should be returned to the treating physician before starting a new therapeutic cycle to assess treatment compliance. Study drug will be supplied by AROG Pharmaceuticals LLC. Study drug may be packaged by a third party. Clinical trial materials will be labeled according to regulatory and institutional requirements.

